6.5.8 Safety & Clinical Follow-Up

To continue collecting data for the safety profile of ^{64}Cu -DOTA-ECL1i a follow up phone call or in person visit to assess for adverse events will occur at least 24 hours following administration of ^{64}Cu -DOTA-EL1i. Taking into consideration both the physical half-life (13 hours) and the much quicker biological half-life optimal follow up time is 48-120 hours post injection but follow up as soon as 24 hours and as late as 14 days post administration are allowed. As this is a verbal secondary assessment follow up phone call or visit beyond 14 days will be accepted with proper documentation of delay(s) such as subject underwent surgical resection and unavailable due to surgery and subsequent recovery. It is anticipated that some subjects may be scheduled for surgery as soon as 12 hours following ^{64}Cu -DOTA-ECL1i administration and imaging so care will be taken to separate surgical related signs and symptoms from those which might be attributed to ^{64}Cu -DOTA-ECL1i administration and PET/CT imaging.

Clinically, subject's medical record will be followed to document surgical resection or the start of definitive therapy.

6.5.9 Immunohistochemical Evaluation of Chemokinetic Receptors

To evaluate the relationship between ^{64}Cu -DOTA-ECL1i uptake and expression of CCR2 receptors in head and neck tumor samples, IHC staining in all patients who have available tissue will be performed using techniques routinely performed in [name] ^{37,38}. Intensity of CCR2 signal in IHC will be assessed by study pathologist, [name] and categorized into 4 categories (0=absent/faint, 1=weak, 2=moderate, 3=strong). Any cells that stained positively with CCR2 will be assessed and the final score will be based on an overall assessment of CCR2 IHC on all these cells. It is anticipated that most subjects will have tumor available from planned surgical resection or prior biopsy however standard of care clinical analysis of resected tumor will take priority over research tissue testing. Tumor testing will occur in batches or at the end of study recruitment depending on availability of testing supplies.

To better understand how CCR2 expression correlates with HPV status and to correlate with samples obtained prospectively a small retrospective tissue analysis study will also be performed. We will obtain tissue from 10 HPV+ and 10 HPV- squamous cell head and neck cancer subjects from the Department of Pathology at Washington University. These samples will be analyzed, as described above, to establish baseline expectations on the correlation of CCR2 expression to HPV status.

6.6.0 Drug Preparation

$^{64}\text{CuCl}_2$ will be produced by the Cyclotron Facility at Washington University School of Medicine, Mallinckrodt Institute of Radiology. ^{64}Cu -DOTA-ECL1i will be produced in the Biologic Therapy Core Facility (ISO 7, class 10,000) at Washington University School of Medicine following SOPs and batch production records. To produce ^{64}Cu -DOTA-ECL1i, $^{64}\text{CuCl}_2$ (20-70 mCi) will be buffered with 20 mM sodium acetate stabilized with gentisic acid and then added to DOTA-ECL1i (30 μg) to bring the total volume to 500 μL (we do not expect any interference with CCR2/5 inhibitor therapeutic effect, because we use a trace amount of

DOTA-ECL1i in comparison to 600 mg therapeutic dose, which is 20,000 higher than the imaging dose). This reaction is incubated in a 45°C heated shaker (ThermoMixer, Eppendorf) for 45 minutes at 950 rpm during which time the DOTA chelator binds with ^{64}Cu . The product will be evaluated by pre-release specifications and post-release specifications to control the quality of the radiotracer for clinical study. This study will be done under an eIND (#137620) for ^{64}Cu -DOTA-ECL1i

6.7.0 Statistics

Demographic and clinical characteristics of the enrolled patients will be summarized using descriptive statistics with frequency and percentages used for categorical variables, median (25th, 75th) for ordinal variables and mean (standard deviation) for continuous variables. The diagnostic quality of images and CCR2 expression detection will be assessed qualitatively and semi-quantitatively for all participants and these measures (described above) will be summarized for a lesion using descriptive statistics. The association between ^{64}Cu -DOTA-ECL1i uptake and tissue signal intensity for CCR2 and other chemokine receptors will be evaluated using a Spearman correlation coefficient. Collection of additional data for the safety profile will not undergo formal statistical review.

The primary goal of this single center, open-label, baseline-controlled diagnostic imaging study is to assess the diagnostic quality and CCR2 expression detectability of ^{64}Cu -DOTA-ECL1i in head and neck cancer patients. The study is primarily descriptive and the sample size is based on feasibility of recruitment. However, a sample size of 20 achieves 80% power to detect a correlation of 0.61 using a two-sided hypothesis test with a significance level of 0.05.

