Figure 1. *Ex vivo* characterization of ^{64}Cu -DOTA-ECL1i binding to CCR2 in human head and neck cancer tissue. (A) H&E. (B) CCR2 DAB staining showed high expression of the receptor in the area full of tumor cells. Control IgG staining confirmed the receptor staining specificity. (C) Autoradiography showed tracer binding to the cancerous area of the tissue and the specificity was verified by the blocking. (D) Quantitative comparison of counts in binding and blocking tissues.

receptors on tumor cells (Figure 1C). The competitive receptor blocking using non-radiolabeled DOTA-ECL1i conjugate in excess amount (DOTA-ECL1i: ^{64}Cu -DOTA-ECL1i molar ratio = 100:1) significantly blocked the binding to the tissue. Quantitative comparison of counts in binding and blocking tissues demonstrated $50.8 \pm 0.6\%$ ($n=4$, $p<0.005$) blocking efficiency (Binding was set as 1 for each specimen), confirming the binding specificity (Figure 1D).

Ex vivo characterization of ^{64}Cu -DOTA-ECL1i binding to CCR2 expressed in human head and neck cancer tissue: CCR2 immunohistochemistry was performed on the de-identified human cancerous tonsil tissue collected from the SCCTPC (Figure 1A). As shown in Figure 1B, strong CCR2 (brown color) signals were detected in the area of tumor cells. Low CCR2 signals were also measured in the muscle and soft tissue, likely due to the expression of the receptors on the infiltrated macrophages or inflammatory cells. The control IgG staining showed negative signal of CCR2, confirming the specific expression of CCR2 on these tumor cells. The *ex vivo* binding assay of ^{64}Cu -DOTA-ECL1i using autoradiography showed strong binding to the cancerous area with signals in similar profile to the CCR2 IHC, indicating the specific binding of the tracer to the CCR2

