6.2.0 Objectives

We are planning to perform a trial with goals to evaluate tumor uptake of ^{64}Cu -DOTA-ECL1i in patients with squamous cell head and neck cancer with at least one measurable lesion of ≥ 1.5 cm. We also will correlate the tumor uptake of ^{64}Cu -DOTA-ECL1i with immunohistochemical staining for CCR2 receptors in the tumor specimens.

Study objectives:

- 6.2.1 To determine the diagnostic quality and CCR2 expression detection rate of ^{64}Cu -DOTA-ECL1i-PET/CT images.
- 6.2.2 To evaluate the relationship between ^{64}Cu -DOTA-ECL1i uptake and immunohistochemical staining for various types of chemokine receptors such as CCR2.
- 6.2.3 To assess the association of CCR2 expression and HPV status. CCR2 immunohistochemical staining in HPV+ and HPV- squamous cell cancer of the head and neck. To better assess the analysis of tissue prospectively we will retrospectively review a limited number of identified samples obtained from the Department of Pathology at Washington University (20 total samples).

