6.5.4 PET Image Processing and Analysis

List mode dynamic PET images will be reconstructed using current scanner manufacturer recommendations as follows (frames x seconds) 12x10, 6x30, and 11x300. PET images will be evaluated qualitatively (graded on a five-point scale regarding the presence or absence of abnormal uptake: 1 = definitely negative; 2 = probably negative; 3 = equivocal; 4 = probably positive; and 5 = definitely positive) and then, semi-quantitatively (standardized uptake value (SUV), tumor-to-normal tissue ratio (T/N) or tumor-muscle-ratio (T/M)) with the knowledge of the location (correlating with all available imaging studies). SUV is a decay-corrected measurement of activity per volume of tissue ($\mu\text{Ci/mL}$) divided by the average activity per unit mass in the entire body. The overall PET image quality also will be graded (using 4-point scale with 1 being the worse and poor quality, not acceptable for diagnostic interpretation and 4 being good image quality, similar to routine clinical studies. PET analysis will not be performed in real time, but performed in batches or after all subjects have been enrolled, however, the images will be evaluated qualitatively for incidental findings.

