The pharmacokinetic of the lesion time-activity curve using graphical analysis and tracer kinetic compartmental modeling will be determined. Classical receptor-ligand models will be employed to describe the kinetics of the tracers and different models to optimize goodness-of-fit will be evaluated. Goodness-of-fit will be judged by a nested F-test for the number of parameters, Akaike Information Criterion (AIC), and the Schwarz Criteria. 1-tissue with two kinetic rate constants and 2-tissue with 4 rate constants compartmental reversible models will be used to fit the data using the blood input function as input function. The blood time activity curve will be determined noninvasively from a large 3D ROI traced over the aorta (OR carotid artery) and corrected for metabolites per above analyses, if available. The measured lesion time-activity curves will be fitted to the 1- or 2-compartment model prediction and added to the plasma component weighted by the tissue blood fraction V_b . Best fit will be used to determine the distribution volume (DV) from the 1-tissue model (with $DV = K_1/k_2$), and we will determine the DV and the non-displaceable binding potential (BP) from the 2-tissue model (with $DV = (K_1/k_2)(1+BP)$ and $BP = k_3/k_4$). The graphical analysis using Logan and Patlak analysis to determine the volume of distribution (DV) also will be performed. We will further use both the plasma time activity curve and a reference region to determined DV and DVR, respectively with non-displaceable BP = DVR -1. A possible region of reference will be a suitably located

muscle in the same field of view as head and neck cancer. All quantitative and semi-quantitative metrics of ^{64}Cu -DOTA-ECL1i-PET/CT will be correlated with CCR2 receptor expression and binding affinity of each biopsy-proven tumor specimen.

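### The planned CCR2 detection rate is computed from PET alone in all participants, so it is a tumour uptake rate; no planned output gives the proportion of CCR2-expressing tumours detected

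*Combined protocol and SAP*

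**What the plan says.** The first objective (6.2.0, item 6.2.1) is "To determine the diagnostic quality and CCR2 expression detection rate of" the tracer's PET/CT images. Section 6.7.0 states the primary goal as "to assess the diagnostic quality and CCR2 expression detectability of" the tracer in head and neck cancer patients.

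For the analysis, 6.7.0 says that "CCR2 expression detection will be assessed qualitatively and semi-quantitatively for all participants and these measures (described above) will be summarized for a lesion". That summary is purely descriptive. The qualitative and semi-quantitative measures are defined in 6.5.4: a five-point visual grade of abnormal uptake, whose upper end reads "3 = equivocal; 4 = probably positive; and 5 = definitely positive", and SUV, tumour-to-normal or tumour-to-muscle ratio. No rule says which grades count as detected or how grade 3 is handled.

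CCR2 in tissue is scored separately (6.5.9) on a 0 to 3 intensity scale in patients with available tissue, where 0 covers absent or faint staining. PET and IHC meet only through correlation. In 6.7.0, the tracer's "uptake and tissue signal intensity for CCR2 and other chemokine receptors will be evaluated using a Spearman correlation coefficient". In 6.5.4, all quantitative and semi-quantitative metrics, which include distribution volume (DV), its ratio to a reference region (DVR) and binding potential (BP), "will be correlated with CCR2 receptor expression and binding affinity of each biopsy-proven tumor specimen".

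The sample size is set by feasibility. The one power statement concerns the correlation: "a sample size of 20 achieves 80% power to detect a correlation of 0.61".

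**The concern.** A detection rate for CCR2 expression should have tumours that express CCR2 in its denominator. The planned figure has every participant there. Patients are not selected for CCR2 (6.4.0), and the IHC scale allows a score of 0. If some tumours are IHC 0, correct non-uptake in them lowers the figure and uptake unrelated to CCR2 raises it.

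At stake is the meaning of the main result. The protocol expects the study to inform how well the tracer evaluates CCR2 expression, with a view to selecting patients for CCR2-targeted therapy (6.8.0). For that purpose a reader needs two proportions: PET-positive among CCR2-expressing tumours, and PET-positive among the rest. Neither is planned, although the data for both will be collected.

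**Working it through.** **1. The plan's own figure.** Inputs from 6.7.0: n = 20, correlation 0.61, two-sided 0.05. With Fisher's z and the usual Spearman variance factor of 1.06:

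power = Φ(atanh(0.61) × √(17/1.06) − 1.960) = Φ(0.709 × 4.005 − 1.960) = Φ(0.879) = 0.81.

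The stated 80% is reproduced. It concerns the correlation and says nothing about the detection rate.

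**2. What the all-participant rate contains.** Let p be the fraction of tumours that are IHC-positive, D the PET-positive proportion among them, and F the PET-positive proportion among IHC-0 tumours. With tissue from everyone, the planned figure is

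U = p × D + (1 − p) × F.

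The IHC scores give p. U and p together leave one equation for two unknowns. U equals D when p = 1, that is, when no tumour is IHC 0.

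**3. Does the planned correlation settle D and F?** The documents give no IHC distribution, so one is assumed: tissue from all 20, with 6, 5, 5 and 4 tumours at IHC 0, 1, 2 and 3 (p = 14/20). Take the 14 highest SUVs as PET-positive. The IHC scores are listed below in ascending SUV order, with the bar marking the PET cut. The last column is Spearman's rho if the yes/no PET call, rather than SUV, is correlated with IHC.

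| IHC in SUV order | D | F | rho, SUV | rho, PET call |
|---|---|---|---|---|
| 0,0,0,0,0,1 \| 3,1,3,1,1,2,2,2,2,0,1,3,2,3 | 13/14 | 1/6 | 0.61 | 0.71 |
| 1,0,0,2,0,0 \| 0,1,1,1,3,3,0,2,2,2,3,1,3,2 | 12/14 | 2/6 | 0.61 | 0.51 |
| 1,1,0,0,0,2 \| 0,1,0,0,3,1,3,3,2,2,1,2,3,2 | 11/14 | 3/6 | 0.61 | 0.40 |

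Check on U: 0.7 × 13/14 + 0.3 × 1/6 = 0.65 + 0.05 = 0.70; 0.7 × 12/14 + 0.3 × 2/6 = 0.60 + 0.10 = 0.70; 0.7 × 11/14 + 0.3 × 3/6 = 0.55 + 0.15 = 0.70. All three data sets report 14/20 and an SUV rho of 0.61 (p = 0.004).

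**4. Exact 95% intervals** (Clopper-Pearson: lower limit from Beta(0.025; x, n − x + 1), upper from Beta(0.975; x + 1, n − x)). U: 14/20, 46 to 88%. D: 13/14, 66 to 100%; 12/14, 57 to 98%; 11/14, 49 to 95%. F: 1/6, 0 to 64%; 2/6, 4 to 78%; 3/6, 12 to 88%.

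**5. Is this spread typical?** In a latent bivariate normal model (correlation 0.60, 0.65 or 0.70; 300,000 data sets each; those with sample rho 0.59 to 0.63 kept), the 14 PET-positive tumours included 1, 2 or 3 of the 6 IHC-0 tumours in 11%, 46% and 37% of data sets, together 94%. None occurred in 0.3% and four or more in 6%. The three rows above therefore cover the usual range.

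**The case against.** **The plan already addresses background signal.** Section 6.5.4 estimates BP and DVR, which are meant to separate binding from background, and correlates them with CCR2 expression. This stands as far as it goes: it would be wrong to infer that the plan has no handle on tumours whose signal mixes CCR2 binding with background. These metrics do not by themselves prove CCR2 specificity, and they yield no proportion of CCR2-expressing tumours detected.

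**The ambiguity depends on which uptake measure is correlated.** This also stands. If the visual call is correlated, the three data sets separate (rho 0.71, 0.51 and 0.40). Section 6.7.0 says only uptake, which could include the grade; 6.5.4 names quantitative and semi-quantitative metrics. Even so, a reader would have to work back to a proportion that the plan could simply report.

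**Uptake in every tumour would not be hidden.** A reader might infer that 20/20 PET-positive with a good correlation conceals uptake in CCR2-negative tumours. It does not: if all tumours are positive and six are IHC 0, then 6/6 follows from the two totals.

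**The ex vivo blocking result is weak support.** Section 6.1.0 reports 50.8% "blocking efficiency (Binding was set as 1 for each specimen), confirming the binding specificity". A reader might infer that the remaining 49.2% shows non-specific uptake in patients. It comes from four ex vivo comparisons, and the documents do not say what the remainder represents in vivo. It is not used here.

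**The remedy is imprecise.** True: the intervals in step 4 overlap heavily, and IHC 0 is an imperfect negative reference. The table still shows directly what the planned outputs leave to inference.

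**The reference to measures above might include IHC.** This is unlikely, because that sentence covers all participants while IHC is done only where tissue exists.

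**Conclusion.** The point holds as one of labelling and interpretation. As written, the detection figure is a tumour uptake rate, and no planned output gives the proportion of CCR2-expressing tumours that PET detects. In the assumed example, the same 14/20 and the same SUV correlation of 0.61 fit detection of 13/14 (93%) with 1/6 IHC-0 tumours positive through 11/14 (79%) with 3/6. Correlating the visual grade would narrow that range.

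The size rests on an IHC distribution that the documents do not give. With tissue from every patient and no IHC-0 tumour, the two rates are identical and nothing is lost. Missing tissue would also make them differ, because the uptake rate keeps patients whose CCR2 status is unknown.

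A reader might go further and infer that the study risks a wrong development decision. The documents do not support that: the study is descriptive, its size is set by feasibility, and no threshold rests on this rate.

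**What to change.** In 6.2.1 and 6.7.0:

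- Label the all-participant figure *tumour uptake rate*.
- Add, as the main display, the full 5-by-4 table of PET grade by IHC score for tissue-matched index lesions, one per patient with tissue.
- From it, report descriptively the PET-positive proportion among IHC-positive lesions as the CCR2 detection rate and, beside it, the PET-positive proportion among IHC-0 lesions, each with an exact 95% interval.
- Define PET-positive as grade 4 to 5, with grade 3 to 5 as sensitivity analysis, and IHC-positive as 1 to 3, with 2 to 3 as sensitivity analysis. Fix these cut-offs before PET and IHC results are linked. Sections 6.5.4, 6.5.9 and 6.9.0 place the main image analysis and the tissue testing in batches or after enrolment, which leaves room for this.
- State the number of patients without tissue.
- Keep the planned correlations.

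The cost is some wording and one table, with no new scan, sample or procedure. The downside is small denominators: if 16 patients have tissue and 5 are IHC 0 (assumed), a perfect tracer would show 11/11 (72 to 100%) and 0/5 (0 to 52%). Because IHC 0 includes faint staining, any single IHC cut-off should stay secondary to the full table.

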6.8.0 Risks and Benefits

Targeting CCR2 is emerging as a promising therapeutic strategy in many types of cancer, but accurate patient selection for this strategy is critical. The potential risks from this imaging protocol are expected to be very low. Expected risks include discomfort from the placement of intravenous catheter(s) for injection of ^{64}Cu -DOTA-ECL1i, radiation exposure from the injection of ^{64}Cu -DOTA-ECL1i and CT for attenuation correction scans, and discomfort from lying still on the imaging table. A temporary altered taste sensation may be associated with the IV injection of ^{64}Cu -DOTA-ECL1i. Blood samples will be obtained for safety profile, whenever possible additional samples are collected for serum stability and metabolites testing. There is a slight risk of bruising and a remote risk of infection from the placement of the intravenous catheter(s). Although unlikely, there is a rare chance of having patients suffer an allergic or other immediate adverse reaction to ^{64}Cu -DOTA-ECL1i. To minimize the risks to subjects, intravenous catheters will only be placed by trained personnel. All studies will take place under the supervision of the Principal Investigator or a collaborating physician. Additionally, the PET scanner is located within the hospital where advanced life support personnel and equipment are available for immediate use.

Radiation Exposure: This research project involves radiation exposure to participants from the i.v. injection of ^{64}Cu -DOTA-ECL1i. The total amount of radiation exposure received from one 10 mCi injection is 0.64 rem. Additional radiation exposure from 2 CT scans for attenuation correction will result in an additional 0.27 rem of exposure (including dose from positioning topogram – 0.09 rem from 1 bed dynamic scan + 0.18 rem from 2 bed limited scan) Total radiation exposure from one 10 mCi injection of ^{64}Cu -DOTA-ECL1i and 2 limited low dose CT scans for attenuation correction is 0.91 rems or approximately 18% of the annual dose for a radiation worker.

The patients entered on this study will not directly benefit from ^{64}Cu -DOTA-ECL1i-PET/CT imaging, the overall and long-term benefits to future patients with head and neck cancer far outweigh the minimal risks anticipated. The minimal risks should be far outweighed by the

potential benefit to society. It is anticipated that this study will contribute to the understanding of the performance of the ^{64}Cu -DOTA-ECL1i-PET/CT in evaluating CCR2 expression in head and neck cancers that will have important impact on the selection of the patients for appropriate mode of therapy. Ultimately, ^{64}Cu -DOTA-ECL1i-PET/CT may provide clinically important information to predict/assess the effectiveness of CCR2-targeted therapy.

The results of the PET imaging studies to be performed as part of the proposed research are not intended to be used in the diagnostic evaluation or treatment planning of individual patients. The results of the PET studies will not be provided to the patient or the treating oncologist or surgeon unless the CT images demonstrate an unsuspected, potentially life-threatening abnormality that warrants further investigation and/or urgent therapy. [name] will assess all imaging results in light of other clinical and radiologic data and will inform the responsible attending physician as soon as possible if the information derived from the experimental imaging studies is judged to be of critical importance to the care of individual patients.

6.9.0 Record Keeping

It is anticipated that 20 subjects will be entered into this study. Initial review of images for quality and uptake will occur in real time with additional analysis performed in batches or after enrollment has been completed. The pathological analysis of the CCR2 will be performed after study enrollment has been completed on the standard of care specimens obtained at surgical resection or from diagnostic biopsy. Data collected to ensure the safety profile of ^{64}Cu -DOTA-ECL1i is accurate will be assessed from the time prior to study drug injection through imaging discharge.

A patient file will be kept in the Research Coordinators' suite located on the 10th floor of the Mallinckrodt Institute of Radiology in Barnes-Jewish Hospital South Campus. All digital data associated with ^{64}Cu -DOTA-ECL1i-PET/CT is maintained on the PET acquisition computer. Raw data files are backed up on password protected encrypted external hard drive(s). All imaging data may also be backed up on DVD after it has been transferred to a desktop PC. Processed data will be stored on the Principal Investigator's password protected desktop. CRF's and patient files will be stored in the study coordinators' office. Entrance to the PI's and coordinators' offices requires admission through two separate locked doors. Standard laboratory assessment (CBC + CMP) will be processed locally with results added to the subjects electronic medical record. ECG's are obtained for study purposes only and are not included in the electronic medical record.

